## HYPOTHESES AND OBJECTIVES

### Overall objective

- To determine the impact in terms of functional recovery, return to pre-hip fracture functional status, of elderly patients treated with the new multimodal therapeutic exercise programme and follow-up for one year compared to patients treated with the previously developed standardised nursing care plan at the Hospital San Juan de Dios de León.

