### Specific objectives

- To describe the improvement in gait ability in patients undergoing hip surgery after a functional recovery programme compared to the historical control group (exposed cohort).
- To describe the clinical and functional characteristics of the patients operated on for hip fracture in the SJD hospital in León who are being followed up by the new system of care implemented in comparison with the historical control group (exposed cohort).
- To analyse risk and protective factors related to the level of dependency and mortality at 30 days and one year of follow-up in patients operated on for hip fracture at the SJD hospital in León.
- To describe the impact of a functional recovery programme on the prevention and treatment of sarcopenia in the new unexposed cohort.
- To describe the quality of life and patient-reported outcomes in the new unexposed cohort.
- To analyse the impact of a functional recovery programme on the prevention of falls in elderly patients who have undergone hip fracture surgery.

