## METHODOLOGY

### Study design

Longitudinal analytical observational study of ambispective cohorts with two groups, an exposed cohort (retrospective) and a non-exposed cohort (protective factor), made up of people over 65 years of age referred from the Emergency Department of the University Care Centre of León (CAULE) to the Hospital San Juan de Dios de León (HSJD) with a confirmed diagnosis of hip fracture and who underwent hip fracture surgery in the latter during the years 2020 and 2021, and who will be followed up during the year after surgery, in the latter, to undergo hip fracture surgery during the years 2020 and 2021 and who will be followed up during the year following the surgery.

Two groups:

- Non-exposed cohort (protective factor): group of patients operated on during the year 2021 in HSJD for hip fracture and to which the new programme implementing functional recovery and therapeutic exercise will be applied with follow-up for one year. The implementation of a functional recovery plan and subsequent follow-up is considered a protective factor in relation to the loss of functionality.
- Exposed cohort (retrospective): complete cohort of patients operated on during the year 2020 in HSJD for hip fracture and to whom no specific functional recovery plan was applied.

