### **Eligibility criteria for the unexposed cohort (protective factor).**

Inclusion criteria:

- Patients referred from the Emergency Department of the Complejo Asistencial de León (CAULE), with confirmation of the medical diagnosis of hip fracture by means of anterior-posterior and lateral radiography.
- Be over 65 years of age.
- Ability to walk before the fracture with or without the aid of instruments or people.
- Have signed the informed consent to participate in the research project.
- With access to a smartphone mobile phone with the option of installing applications.

Exclusion criteria:

- Polytrauma patients will be excluded.
- Metastatic origin of the fracture.
- Periprosthetic fracture.
- Patients with cognitive impairment that makes it impossible for them to use the PPP and who are not accompanied by a responsible person during the recovery process.

Withdrawal criteria:

- Mortality at hospital discharge.
- Presentation of complications.
- Non-compliance with the therapeutic plan or assessment process.

**Eligibility criteria** for the exposed (retrospective) cohort.

Inclusion criteria:

- Patients referred from the Emergency Department of the Complejo Asistencial de León (CAULE), with confirmation of the medical diagnosis of hip fracture by means of antero-posterior and lateral radiography.
- Be over 65 years of age.
- Ability to walk before the fracture with or without the aid of instruments or people.

Exclusion criteria:

- Polytrauma patients will be excluded.
- Metastatic origin of the fracture
- Periprosthetic fracture.

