This programme is divided into 5 phases, each of these phases coincides with a level of the gait assessment scale. Each individual will start at the level assigned by the doctor and will only have access to the videos of the indicated level and the levels below it. As the patient meets the recovery goals, the physician will provide access to the higher level videos. The functional recovery plan begins the day after the hip fracture and continues after the patient has been discharged for a total of 16 weeks.

- The therapeutic plan for the historical control group (standard practice until 31 December 2020) consisting of postural changes described in the standardised nursing care plan. Within this plan, the patient was moved to a sitting position prematurely (within the first 24 hours) and started to ambulate within the following 48

hours, provided that the patient's general condition allowed it. This group did not receive any specific functional recovery plan.

- The patient is discharged from hospital and will be assigned a link where he/she will be able to access the online platform to send information from the questionnaires sent during the established periods of 1, 3, 6 and 12 months and will also be sent videos illustrating the rehabilitation exercises that he/she will have to perform during this period. The patient and/or carer will be explained how the tool works, how to access the digital information content and how to access the questionnaires. A means of contact will be provided to resolve doubts, if any. The PI will have access through the web/app platform to a control panel where he/she will be able to detect a patient's lack of adherence, if any, or alerts related to clinical evolution, allowing for exhaustive monitoring of the patient.
- Analysis of results: The data collected will be analysed with the SPSS programme. The mean, median and standard deviation of each of the variables will be calculated. Based on the data obtained from the existing literature(31), having selected a sample of 67 patients, a normal distribution can be assumed for all variables  
For baseline demographic and clinical characteristics, a comparison of means for quantitative variables (t-Student), and of proportions (Chi-square) for qualitative will be performed  
The statistical analysis will be carried out with a confidence level of 95%, so that statistically significant values will be considered to be those whose probability is < 0.05.

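### No outcome analysis, analysis set or adjustment is given for the 2021-versus-2020 recovery comparison, although several selection and all withdrawal rules apply to 2021 only; whether 2020 has follow-up mobility must be settled first

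*Combined protocol and SAP*

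**What the plan says.** The Overall objective is a between-cohort contrast: "return to pre-hip fracture functional status, of elderly patients treated with the new multimodal therapeutic exercise programme", set against patients who received the earlier nursing care plan. The Hypothesis section expects the programme to do better. In the plan's terms, the 2021 patients are the unexposed cohort and the 2020 patients the exposed, retrospective one.

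The statistical text is the item on analysis of results in the Work plan, under Description of the process. It gives the mean, median and standard deviation of each variable, a statement that a sample of 67 allows normality to be assumed for every variable, a 0.05 threshold, and these tests: "For baseline demographic and clinical characteristics, a comparison of means for quantitative variables (t-Student), and of proportions (Chi-square) for qualitative will be performed".

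The eligibility section has separate lists for the two cohorts. Age, diagnosis, walking ability before the fracture, and the polytrauma, metastatic and periprosthetic exclusions are common to both. The 2021 list alone adds:

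- signed consent;
- "With access to a smartphone mobile phone with the option of installing applications";
- an exclusion: "Patients with cognitive impairment that makes it impossible for them to use the PPP and who are not accompanied by a responsible person";
- three withdrawal criteria: "Mortality at hospital discharge", the occurrence of complications, and "Non-compliance with the therapeutic plan or assessment process".

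Limitations of the study names the pandemic and the lack of randomisation. No analysis step follows from either.

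**The concern.** Testing baseline differences does not correct for them, and nothing else is specified. The analyst is left to choose the outcome definition, time point, analysis set and adjustment after the data are in. Meanwhile the 2021 rules tend to take out people with a poorer outlook (deaths, complications, unaccompanied cognitive impairment) on one side only. A difference in favour of 2021 could then reflect who was counted rather than the programme.

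A prior question is whether the 2020 data contain any mobility measurement after admission. If they do not, no model can answer the main objective.

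**Working it through.** **1. No planned figure to reproduce.** The 67 comes with no effect size, event rate, power, allocation ratio or dropout rate, and the text does not say whether it is a total or a number per cohort.

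**2. Effect of losing patients from 2021 only.** Let p be the true recovery rate in both years (no programme effect), w the share of 2021 patients removed, and r the recovery rate among those removed. The retained 2021 rate is (p − wr)/(1 − w), so the spurious gain is w(p − r)/(1 − w).

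Inputs: p = 50% is a Background figure given without a time point, so 30% is shown as well. The documents do not give w or r; both are assumed. Setting r = p/2 means those removed recover half as often as average. Setting r = 0 is an upper bound, and it also assumes that 2020 keeps its corresponding patients.

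| p | w | r = p/2 | r = 0 |
|---|---|---|---|
| 50% | 10% | 0.10×0.25/0.90 = 2.8 points | 0.10×0.50/0.90 = 5.6 |
| 50% | 20% | 0.20×0.25/0.80 = 6.3 | 0.20×0.50/0.80 = 12.5 |
| 30% | 10% | 0.10×0.15/0.90 = 1.7 | 0.10×0.30/0.90 = 3.3 |
| 30% | 20% | 0.20×0.15/0.80 = 3.8 | 0.20×0.30/0.80 = 7.5 |

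If in-hospital deaths (5%, assumed) drop out of both cohorts and 2021 loses a further 5% or 15% who would not recover, the gap is p/(1 − 0.05 − e) − p/(1 − 0.05). At p = 50% this is 55.6 − 52.6 = 2.9 points (from unrounded rates) or 62.5 − 52.6 = 9.9. At p = 30% it is 1.8 or 5.9. If r = p there is no bias.

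**3. What the documents say about 2020 follow-up.**

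- For: the first group of variables (National Hip Fracture Registry) is said to be given to both groups. The RNFC mobility scale and mFAC, described there, are scheduled at admission, 6 weeks, 4 months and 1 year. Study design describes patients operated on in 2020 and 2021 "who will be followed up during the year after surgery", although that sentence is garbled and repeats itself.
- Against: the same first-group section calls its variables characteristics before surgery and takes the 2020 values from an existing file. The Variables section says that until now follow-up ended after one month. The second group, measurable only in 2021, contains follow-up RNFC, follow-up mFAC and death (a complication code in Table II).
- Death is also unclear because one specific objective is "To analyse risk and protective factors related to the level of dependency and mortality at 30 days and one year of follow-up", with no restriction to 2021.

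These statements cannot all hold.

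**4. Timing.** If 2020 ends at about 30 days and the first scheduled 2021 mobility value is at 6 weeks, the gap is 42 − 30 = 12 days, provided both run from the same event. Sampling counts the 2021 visits from discharge. If the 2020 month runs from surgery or admission, the gap is longer. The programme itself lasts 16 weeks.

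**5. Normality.** Sex, caregiver status, fracture side, RNFC and mFAC are categorical or ordinal. No sample size makes such variables normal.

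**6. Model size.** A logistic model with cohort (1), pre-fracture mobility in three groups (2), age (1), sex (1), Pfeiffer (1) and caregiver (2) has 8 parameters. Dropping sex and caregiver leaves 5. At an assumed 10 recoveries (or non-recoveries, if fewer) per parameter, the full model needs 80/0.5 = 160 or 80/0.3 = 267 patients in total. The reduced model needs 50/0.5 = 100 or 50/0.3 = 167. A total of 67 supports neither; 67 per cohort (134) supports only the reduced model, and only at 50%.

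**The case against.** The best defence is that this is an observational, real-world study that admits its limits, describes itself as a complete-cohort analysis, and could extend its chi-square test to recovery. Withdrawal might mean leaving the programme rather than leaving the analysis. Some of this stands. The plan never says that withdrawn patients are dropped, so the bias depends on how the missing analysis set is filled in. Non-compliers might also recover as well as others, or better, which would shrink or reverse that part of it. But a stated hypothesis of better results needs a stated comparison, and a crude chi-square would still carry the selection at enrolment.

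Three stronger readings are tempting, and the documents do not support them:

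- *2020 has no follow-up mobility data, so the objective cannot be answered.* The statement that the scales go to both groups, with a schedule to one year, is direct evidence the other way. The text conflicts; it does not settle the matter.
- *67 contradicts the complete-cohort design.* Cohort sizes are not stated, so no numerical conflict exists. Only the wording (a selected sample versus everyone) needs explaining.
- *Averaging RNFC, with Unknown coded as level 11, distorts the main result.* RNFC is typed as qualitative and no outcome analysis uses its mean, so this touches descriptive summaries only.

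It is also fair to say that the choice between RNFC and mFAC is a judgement, and that adjustment cannot remove the calendar-year effect.

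**Conclusion.** The point holds and should be settled before outcomes are compared. The plan gives no outcome analysis, analysis set or adjustment for its main between-cohort objective, and the one-sided 2021 rules would tend to favour 2021 under a crude comparison or one without the withdrawn patients. The plausible size runs from about 2 to 6 points when those lost recover half as often as average, up to a bound of 12.5, for losses of 10% to 20% and recovery of 30% to 50%. The loss shares, the recovery among those lost and the 30% are assumptions; the 50% is a background figure. The direction assumes that those lost recover less often than average. Whether the objective can be answered at all depends on the 2020 file, which the documents leave unresolved. The normality sentence is wrong, but a minor matter.

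**What to change.** 1. Check the 2020 file for follow-up RNFC and mFAC, their dates, and deaths. Reconcile Study design, Variables, the first and second groups of variables and Table II. Name one scale and one follow-up time that both cohorts have, counted from the same event. If 2020 has no follow-up mobility value, state that the between-cohort objective cannot be answered, and do not impute it. If only about one month and 6 weeks are available, state that the gap favours 2021 and that the result describes a partly delivered 16-week programme, not one-year recovery.
2. Make the main analysis a logistic model of mobility at follow-up no worse than before the fracture, on cohort, adjusted for pre-fracture mobility (grouped in advance), age, sex, Pfeiffer score and caregiver. All are listed for both cohorts. Report the adjusted odds ratio and risk difference with 95% confidence intervals. Fix a reduced set, and choose between the two on counts before outcomes are compared. If counts support neither, use penalised logistic regression with the reduced set, or report the unadjusted risk difference and its interval as descriptive only.
3. Keep every enrolled 2021 patient in the analysis, including those with complications or non-compliance. Count deaths as not recovered if both cohorts record them. If 2020 does not, compare survivors in both and state that limit.
4. Treat RNFC level 11 as missing. Apply one rule for missing follow-up mobility to both cohorts: multiple imputation from baseline variables, with a sensitivity analysis counting missing as not recovered. Report missing counts by cohort and reason.
5. Report how many patients operated on in 2021 were not enrolled, and why. State that calendar year and the pandemic, smartphone access and consent remain as residual confounding.
6. Delete the normality sentence, summarise RNFC and mFAC by level and median, and say what 67 refers to.

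Cost: one check of an existing file, some plan wording and a few hours of analysis on variables already listed. The price is a less precise estimate if the cohorts are small.

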**Table I: Sociodemographic, clinical and functional characteristics prior to surgery.**

Variables	Unit of measurement	Type
Age	Years	Independent quantitative
Genre	H- Male M- Female	Independent qualitative
Caregiver	1- Yes 2- No 3- Live alone	Independent qualitative
Preoperative mental assessment. Pfeiffer Test (SPMSQ-VE)	Points (0 to 10)	Qualitative
Mobility RNFC ladder	Levels (1 to 11)	Qualitative
Pre-fracture mobility. Gait assessment scale (mFAC).	Levels (0 to 6)	Qualitative
Side affected by the fracture	D- Law I- Left	Qualitative
Abbreviations: SPMSQ-VE: Short Portable Mental Status Questionnaire, (mFAC): Modified Functional Ambulatory Classificator, RNFC: Registro Nacional de Fractura de Cadera.		

- **Preoperative mental assessment. PfeifferTestor "Short Portable MentalStatusQuestionnaire" (SPMSQ-VE) (32)**

It assesses the patient's cognitive status at the time of administration. It consists of 10 questions that are asked prior to surgery, inwhich errors are computed. The test should be performed as close to the patient's baseline cognitive state as possible.

The inter- and intra-observer reliability of the SPMSQ-VE is 0.738 and 0.925 respectively, with an internal consistency value of 0.82 (32)

Pfeiffer test translated and validated in Spanish

1. What day is today? (Month, day, year).
2. What day of the week is today?
3. Where are we now?
4. What is your telephone number? (If no telephone, street address).
5. How old are you?
6. What is your date of birth?
7. Who is the current Prime Minister?
8. Who was the previous Prime Minister?
9. Tell me your mother's first surname.
10. Starting at 20, subtract 3 by 3 successively until you reach 0.

Errors are scored, 1 point per error. A score of three or more indicates cognitive impairment. If the educational level is low (elementary education), one more error is allowed for each category. If the level of education is high (university), one level less is allowed.

This scale is only administered prior to surgery to assess the patient's cognitive status.

This scale is administered on entry.

- **Pre-fracture mobility, according to the national fragility hip fracture registry(33).**

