Gait is the parameter most strongly associated with frailty states, with gait speed being the parameter most commonly associated with frailty(34,36). This is why it is so important to recover functions and capacities in this area of movement. This scale is very easy to use and apply and is used by the national fracture registry, which allows us to make comparisons and statistical analyses with the results published with this registry.

It assesses by ability levels ranging from 0 to 11. Its design allows firstly to determine gait ability and secondly to see the evolution and establish treatment guidelines.

Capacity levels:

- Level 1-Independent mobility inside and outside the home without technical aids
- Level 2- Independent mobility inside and outside the home, with technical assistance.
- Level 3- Independent mobility inside and outside the home with two technical aids or walker.
- Level 4- Independent mobility only indoors without technical assistance.
- Level 5- Independent mobility only indoors with a technical aid.
- Level 6- Independent mobility only indoors with two technical aids or walker.
- Level 7- Independent mobility only within the house under personal supervision.
- Level 8- Mobility only within the home with little assistance from a person.
- Level 9- Mobility only within the home with a lot of help from a person.
- Level 10- Mobility with two people or no mobility.
- Level 11- Unknown.

For simplicity this variable is summarised in these questions:

- Technical aids (yes/no).
- Outside/inside the home.
- And note the best situation, i.e. it is better with a cane outside than without help at home.

This scale is administered at admission, 6 weeks, 4 months and 1 year.

• ***ModifiedFunctionalAmbulatoryClassifier(mFAC)(36).***

It is a scale that assesses different levels of ability by grading them between 0 and 6. Its design allows firstly to determine gait ability and secondly to see the evolution and establish treatment guidelines. The modified gait assessment scale has shown an intraclass correlation coefficient(ICC)= 0.960, with a 95% confidence interval: 0.942-0.972, an inter-observer agreement Cohen's kappa index of 0.83 (CI: 0.69-0.97) and a validity p= 0.814 (36-38)

The capacity levels for this scale are:

- Level 0: Patient who cannot remain seated for more than 1 minute without the help of the backrest and armrest.
- Level 1: Patient who can remain seated without the aid of the backrest and armrest for more than 1 minute.

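### Three ordered baseline scales (Pfeiffer, RNFC mobility, mFAC) are typed as qualitative and so compared by a chi-square that ignores level order, which loses power against a shift between the cohorts; the size of the loss depends on a cohort size the plan does not give

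*Combined protocol and SAP*

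**What the plan says.** The analysis bullet under Description of the process (Work Plan) gives one rule for baseline demographic and clinical characteristics: "a comparison of means for quantitative variables (t-Student), and of proportions (Chi-square) for qualitative will be performed". No rank, trend or ordinal method is named in the document. The significance threshold is 0.05.

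The variable type therefore decides the test, and Table I sets the type:

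- Pfeiffer, a count of errors: "Pfeiffer Test (SPMSQ-VE) Points (0 to 10) Qualitative"
- RNFC mobility: "Mobility RNFC ladder Levels (1 to 11) Qualitative"
- mFAC: "Gait assessment scale (mFAC). Levels (0 to 6) Qualitative"

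The text after Table I treats all three as graded. Pfeiffer errors are added up. The RNFC and mFAC levels are described as grades for following a patient's progress, and raters are told which of two RNFC situations counts as better. The last RNFC code is the exception: "Level 11- Unknown".

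The same analysis bullet also promises a mean, median and standard deviation for each variable and assumes normality for all of them. That sits badly with the qualitative typing, but it does not alter the test assigned by type.

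**The concern.** A Pearson chi-square on a 2 x k table tests whether two unordered profiles are equal. Shuffling the level labels leaves the p-value unchanged. The baseline question is directional: did the patients of one year walk or think better before the fracture than those of the other? A test that uses the order concentrates its power on that question.

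It matters here for three reasons. The main objective is return to pre-fracture functional status, so pre-fracture mobility is the reference for the outcome. The cohorts are not randomised, as the limitations section acknowledges. And the eligibility criteria differ: only the 2021 cohort needs smartphone access and signed consent, and only it excludes cognitively impaired patients who cannot use the tool and have no responsible companion. A shift in cognition, and perhaps in mobility, is foreseeable. The plan describes no adjusted comparison, so these baseline tests are the only comparability check it states.

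**Working it through.** **Inputs from the plan.** Test rule and 0.05 threshold (analysis bullet; two-sided assumed, as sidedness is not stated). Scale ranges and types (Table I). Ability to walk before the fracture (eligibility criteria), which on a plain reading leaves about 5 usable mFAC levels (2-6) and about 9 RNFC levels (1-9). A sample of 67 (analysis bullet), not said to be per cohort or in total. Complete cohorts of unstated size (Sampling).

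**The plan's own figure.** The 67 cannot be reproduced. It is given only to justify normality, without effect size, SD, power or allocation. For reference, a two-sample comparison of means at 0.5 SD would have 82.5% power with 67 per cohort and 53.4% with 67 in total.

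**Assumptions.** A normal latent score with a 0.5 SD shift, cut into levels that are either equally likely or skewed. The documents supply neither the shift nor the distributions.

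**Why order matters.** With n per cohort and level probabilities p and q, the chi-square noncentrality is n x sum of (p - q)^2/(p + q), on k - 1 degrees of freedom. For ten equally likely levels and a 0.5 SD shift the sum is 0.1136.

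- Chi-square, 67 per cohort: 67 x 0.1136 = 7.61 on 9 df, critical value 16.92, power about 43%.
- Comparison of means on the latent score: n x d^2/2 = 67 x 0.25/2 = 8.38 on 1 df, critical value 3.84, power 82.5%.

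The signal is similar in both. The chi-square spreads it over nine degrees of freedom.

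**Simulation.** 4,000 data sets per scenario (Monte Carlo standard error at most 0.8 points). Power in %, Pearson chi-square versus Mann-Whitney with tie correction, 0.5 SD shift:

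| Scale (levels assumed) | 67 in total | 67 per cohort | 100 per cohort | 200 per cohort |
|---|---|---|---|---|
| mFAC (5 or 7) | 24-27 vs 45-48 | 48-56 vs 74-77 | 70-76 vs 89-92 | 97-98 vs over 99 |
| RNFC (9 or 10) | 18-19 vs 49-50 | 42-46 vs 78-80 | 63-65 vs 92-93 | 95-96 vs over 99 |
| Pfeiffer (11) | 16 vs 48-49 | 38-39 vs 79-80 | 59-61 vs 92-93 | 93-95 vs over 99 |

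The loss is about 18-33 points with 67 in total, 20-40 with 67 per cohort, and 1-7 with 200 per cohort. For a smaller shift of 0.4 SD at 200 per cohort, power is 77-87% versus 95-98%.

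**Error rate.** With no shift the chi-square rejects in 3-6% of data sets and the ordered test in 4-6%. The lower power does not buy tighter error control.

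**If the scales are collapsed, 67 per cohort.** RNFC as outdoors/indoors gives chi-square power of 53-61%, against 77-80% for an ordered test on all levels. Pfeiffer cut into impaired or not (assumed 35-48% impaired) gives about 61% against about 79%. The loss is therefore between 77 - 61 = 16 and 80 - 53 = 27 points.

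**The case against.** The strongest reply is that the size of the effect is not in the documents. The 67 carries no allocation, while the Summary, Study design and Sampling sections speak of analysing complete cohorts. If those reach about 200 each, a half-SD imbalance is missed in 2-7% of cases by chi-square and in under 0.5% by an ordered test, which has little practical weight. If 67 is the total, the ordered test itself misses 50-55%, so changing the test does not produce a dependable check. This stands, and it is why only a range can be given.

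Second, the plan may not intend tables with nine or ten degrees of freedom. The RNFC text says the variable is summarised by use of aids and by outside or inside the home, and the Pfeiffer text gives a cut-off of three errors. The plan does not say which form enters the baseline comparison, and comparing proportions fits collapsed categories as well. This narrows the loss but does not remove it.

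Third, a reader might infer that a non-significant baseline test will be taken as proof that the cohorts are alike. No passage says so, and none makes the outcome comparison conditional on these p-values. That misuse is a risk, not something the plan states.

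Fourth, if comparability is judged from standardised differences, the choice of test matters less. That is true, and it is part of the fix. The stated rule would still assign an unsuitable test to the variables closest to the outcome.

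**Conclusion.** The point holds as a correctable choice of method. The typing in Table I and the test rule together send three ordered scales to an unordered test, and in every scenario tried this lost power against a shift.

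The amount rests on an assumed shift, assumed level distributions and an unstated cohort size. It is substantial at 67 per cohort or 67 in total and small for a 0.5 SD shift at 200 per cohort. A reader might conclude that a half-SD imbalance would be missed two to three times as often. The simulated ratio is indeed about 1.9 to 3.0 at 67 per cohort on the full scales, but the documents establish neither that cohort size nor that the full scales are tabulated, so it cannot be stated as a property of this study.

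Nor does the point show that the outcome comparison is biased. It concerns how well the stated baseline check can see an imbalance. Confounding between the 2020 and 2021 cohorts remains whichever baseline test is used, and an adjusted outcome analysis would matter more for that.

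**What to change.** - Type RNFC mobility and mFAC as ordinal in Tables I and II, and Pfeiffer as ordinal in Table I (it does not appear in Table II).
- In the analysis bullet, compare these three scales between cohorts with Mann-Whitney or a proportional-odds model. Keep chi-square for sex, caregiver and side.
- Treat RNFC level 11 as missing and report its frequency by cohort. Otherwise an unknown status would be ranked as the worst mobility.
- Report a standardised difference with its 95% confidence interval for every baseline variable, and judge comparability from these, not from p < 0.05.
- Reconcile the normality assumption and the promised means for all variables with the new typing.

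The cost is a few words in two tables and a short change to one paragraph. No new data are needed, and the scores are collected whichever test is used. One small downside is that an ordered test is less sensitive to a difference in spread without a shift.
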